1. RESEARCH STRATEGY

Colorectal cancer (CRC) is the third most common type of cancer in the U.S.,¹ and diet is a recognized risk factor. Overall, CRC incidence and mortality rates have decreased in the past 20 years, attributed largely to use of CRC screening and polypectomy in adults over 50 years and improved therapy options. However, among adults younger than 50 years, for whom screening is not recommended if at average risk, CRC incidence rates have been increasing by ~2% per year since 1994 in both men and women.¹ While genetic factors account for some of the risk, environmental factors account for the majority of CRC risk.² Observational studies show inverse associations between dietary fiber and CRC risk,³⁻⁶ with significant risk reduction found primarily in groups with fiber intakes >25 g/d.⁷

CRC risk, in addition to hyperplastic and precancerous adenomatous polyps,⁸ could be greatly reduced through dietary modification, including increased dietary fiber intake and reduced intake of certain types of fat.⁹ In the 2011 Colorectal Cancer Report, part of the Continuous Update Project, the World Cancer Research Fund/American Institute for Cancer Research Expert Panel classified evidence supporting consumption of fiber-containing foods and CRC protection as 'convincing'.¹⁰ The Panel noted that for every 10 g/d increase in fiber, there was a 10% decrease in CRC risk. This recommendation was based on recent systematic reviews and meta-analyses of prospective cohort studies, which together showed significant CRC risk reduction with greater fiber intakes.^{11, 12} Inconsistencies across epidemiologic studies are attributed in part to lower overall fiber intakes and narrow ranges of fiber intakes in Western populations.¹³ For example, among ~135,000 women in the Women's Health Initiative (WHI) cohort, <10% of participants reported fiber intakes >25 g/d, with the majority of intakes falling between the narrow range of 10-20 g/d.¹⁴ In fact, <5% of all Americans meet the recommended intake for dietary fiber, with mean intake ~15 g/d.^{8, 15} As Bingham and others have pointed out, reductions in CRC are only apparent with fiber intakes >25 g/d.⁷ Intakes at or above current recommendations (28 g/d for women and 35 g/d for men) show robust protection against CRC with relative risks ranging from 0.72 to 0.90.^{8, 11, 12, 14} Animal models have also corroborated that dietary fiber reduces colon tumorigenesis.¹⁶⁻¹⁸

Several mechanisms have been hypothesized to explain how dietary fiber may reduce CRC. These include fiber fermentation to short-chain fatty acids (SCFA), particularly butyrate, by gut microbiota, reduced microbial production of secondary bile acids, faster intestinal transit time, and increased stool bulk.¹⁹⁻²¹ Given the potential importance of fiber fermentation, consideration of fiber subtypes (i.e., soluble and insoluble or more and less fermentable) and their different microbial fermentation capacity to generate butyrate may be important. Few studies in humans have looked at fiber subtype and reports indicate both null^{14, 22, 23} and inverse associations.²⁴⁻²⁷

[figure not shown]
Diet may affect CRC risk by contributing particular substrates (e.g., dietary fiber) that allow for production of chemoprotective microbial metabolites and modulating specific species in the gut microbiota.²⁸ For example, a key factor in determining the availability of butyrate and setting apoptotic and other regulatory events in motion is gut microbial fiber fermentation. Types of complex carbohydrates consumed (e.g., dietary fibers, resistant starch) influence prevalence of certain consortia of gut bacteria and subsequent metabolites to which the host is exposed.²⁹⁻⁴² The microbiome responds rapidly to dietary interventions,⁴³ although individual responses may differ.⁴⁴⁻⁴⁷ Bacteria ferment fiber to SCFA, predominantly acetate, butyrate, and propionate, in a ratio of 3:1:1⁴⁸ via metabolic pathways unique to anaerobic gut bacteria.⁴⁹⁻⁵² Butyrate producers form a functional cohort, rather than a monophyletic group, distributed across four different phyla: *Firmicutes*, *Fusobacteria*, *Spirochaetaceae*, and *Bacteroidetes*.⁵³ Butyrate is produced via multiple pathways: the acetyl-CoA,^{54, 55} glutarate,⁵⁶⁻⁵⁸ 4-aminobutyrate,⁵⁹⁻⁶¹ and lysine pathways,⁶²⁻⁶⁴ but distribution of these pathways in the human microbiome varies.⁵³ The dominant pathway associated with butyrate production is the acetyl-CoA pathway. The last step in conversion to butyrate across these multiple pathways is carried out by butyryl-CoA transferase (*but*) and butyrate kinase (*buk*).^{53, 65-67} Vital et al⁶⁸ suggested that targeting the 21 human microbiome genes involved in butyrate production across these four pathways gives a comprehensive picture of microbial butyrate production or "butyrogenic potential." Propionate is also a major fiber fermentation product that can induce

Randomized, Controlled Trial of Resistant Starch in Stage I-III Colorectal Cancer Survivors Pilot Study: The Fiber for Health After Cancer Study

differentiation and apoptosis.⁶⁹⁻⁷¹ Bacteria across several phyla produce propionate through the succinate and acrylate pathways.⁷²⁻⁷⁵

Preliminary Data and Experience in Support of Proposed Microbiome Analysis. Gut microbiome studies directed by [name] have focused on measurement of GMC using sequence-based high-throughput methods, metagenomic approaches. We have optimized methods for fecal bacterial DNA preservation and extraction, and GMC analysis^{76, 77} and applied these to studies of diet and the gut microbiome.^{76, 78, 79} **GMC is altered by dietary fiber.** Directly relevant to our proposed study, we compared GMC in response to 28 d of controlled refined grain and whole grain diets (25 & 48 g fiber/d, respectively).⁸⁰ We analyzed stool samples collected at baseline and the end of 2 diet periods, characterizing GMC by sequencing the V1-V3 region of the 16S rRNA gene. In total, we analyzed ~2 million sequences. After trimming, we identified bacteria using 700,000 high quality sequences for analysis.⁸¹ Linear discriminant analysis (LDA) showed GMC differences between baseline and the 2 diets (**Figure 1**) and GMC was different between the 2 diets (perMANOVA, $F=1.3$, $p<0.03$, $n=25$) Further analysis showed an enrichment in Parabacteroides on the whole grain diet (**Figure 1**) whereas the refined grain diet enriched for Clostridiales.

Figure 1. Linear discriminant analysis of the microbiome at the end of the whole grain (WG, Green) and refined grain (RG, Red) dietary interventions.

Microbial butyrate-production genes

are associated with carbohydrate intake. 16S rRNA genes. In 107 women, we evaluated associations between diet and GMC (pyrosequencing of V1-V3 region of 16S rRNA gene).⁷⁸ We analyzed ~1.4 million sequences. After trimming, we identified bacteria in 644,956 high-quality sequences.⁸¹ Using 3-d food records, we detected differences in GMC structure between participants with low and high intakes (tertile 1 & 3) of refined grains ($p<0.0001$), starch ($p<0.003$), and insoluble fiber ($p=0.034$; Multi-Response Permutation analysis).^{82, 83} Based on 16S rRNA gene content, we estimated the microbiome functional gene content.⁸⁴ There was significant enrichment in functional genes associated with the butyrate-production pathway in participants with higher fiber intakes (t-test, $p=0.037$).

The average U.S. consumption of dietary fiber is only 20-50% of recommended intake levels. Resistant starch (RS) is a naturally occurring type of fiber that is resistant to human digestion, but may be fermented by the human gut microbiota and affect systemic markers of health. RS is associated with decreased insulin resistance, systemic markers of inflammation, and serum endotoxin levels in both animal models and humans. Our aim is to see if a 2 months regime of eating common foods made with RS will change markers of inflammation and insulin resistance as well as the composition of gut bacteria in colorectal cancer survivors.

Study Overview

Patients with a history of stage I-III colorectal cancer who have completed colorectal cancer treatment will be recruited from the SCCA GI Oncology Clinic. Patients will participate in an 8-week randomized, controlled trial testing foods made with resistant starch vs foods made with corn starch. All food products will be made under strictly controlled conditions in the Fred Hutch Human Nutrition Lab and will include a variety of common foods such as scones, muffins, pudding and cookies. The only difference between the products is that some products will be made with resistant starch and some will be made with corn starch. Both investigators and participants will be blinded to their randomization assignment.

Randomized, Controlled Trial of Resistant Starch in Stage I-III Colorectal Cancer Survivors Pilot Study: The Fiber for Health After Cancer Study

Eligibility criteria include: 1) history of diagnosed AJCC stage I-III colorectal adenocarcinoma; 2) completion of all treatment of colorectal adenocarcinoma within the past 4-36 months; 3) ECOG Performance Status of 0, 1, or 2 (per physician); 4) age ≥ 18 years at diagnosis; 5) absence of any active inflammatory bowel disorder; 6) no use of antibiotics within 3 months prior to enrollment; and 7) ability to consent and follow study protocol.

Stool sample will be collected three times in the privacy of each person's home using a kit and instructions provided. Fasting blood samples will be collected at baseline and week 8 at the Fred Hutch Prevention Center.

After agreeing to participate and signing informed consent, participants will be randomized to receive the active intervention (daily foods containing resistant starch) or control intervention (daily foods containing corn starch).

The intervention will use commercially available RS-2 (Hi-Maize) that will be prepared into common bakery items, such as muffins, scones, as well as beverages such as smoothies. Control products will use the same recipe but will be prepared with regular corn starch. The RS will be Hi-Maize, a corn starch made solely from hi-amylose maize. This product is commercially available from, among others, King Arthur Flour, Honeyville and Amazon. It has been used in many published studies⁸⁵⁻⁹³ as well as at least 20 studies currently listed in ClinicalTrials.gov. Dose range has been from 15g/day to 47g/day and study duration from 1 to 8 weeks. Some people may experience flatulence and perhaps some bloating due to the higher fiber content added to their diet, therefore we will have participants do a stepwise escalation that will allow for better adaptation to the target dose of 30g. RS per day. In the first two weeks participants will consume one study food with 15 g RS per day and starting in the third week participants will consume two study foods for a total of 30g RS per day for 6 weeks. Participants will be provided with a variety of options to allow for variety. No other dietary changes will be required. Participants may consume their usual diet and participate in their usual activity throughout the study. All products will be produced at the Human Nutrition Lab in the Fred Hutch Prevention Center. See Figure 2.

Systemic inflammation will be measured as serum C-reactive protein (CRP)/albumin ratio and adiponectin. Insulin resistance will be assessed using the homeostasis model of assessment-insulin resistance (HOMA-IR). Gut microbial community structure (16S rRNA sequencing), and gut metabolites will be compared between intervention and control groups for generation of hypotheses for protective prebiotic effects on gut microbial taxa.

In order to determine whether an RS dietary intervention can potentially affect gastrointestinal tumorigenesis in high-risk individuals, participant fecal microbiota sampled will be transplanted into colorectal tumor-prone mice ([name], UW IACUC protocol # 4418_01).

[figure not shown]
Primary Aim: To determine the feasibility of an 8-week dietary intervention testing foods made with resistant starch compared to foods made with corn starch in patients who have completed treatment for stage I-III colorectal cancer. Feasibility will be assessed based on trial accrual, intervention adherence, and trial retention.

Secondary Aims:

1. To assess variability from baseline to 8 weeks in circulating markers of insulin resistance (glucose, insulin and HOMA-IR) and inflammation (CRP, albumin, adiponectin), by randomization arm.
2. To assess variability from baseline to 2 weeks and 8 weeks in gut microbial communities based on 16S rRNA gene sequencing, by randomization arm.
3. To explore whether resistant starch suppresses adenomas/carcinomas in human to mouse Fecal Microbiota Transplantation (FMT) studies.

Randomized, Controlled Trial of Resistant Starch in Stage I-III Colorectal Cancer Survivors Pilot Study: The Fiber for Health After Cancer Study

Figure 2 – Study Design. Note: The Stool Only protocol and companion Intervention Pilot have separate protocols and IRB submissions. [name], Co-PI, will receive human fecal samples for the gnotobiotic mouse experiments under IACUC approval (UW IACUC protocol # 4418_01).

Randomized, Controlled Trial of Resistant Starch in Stage I-III Colorectal Cancer Survivors Pilot Study: The Fiber for Health After Cancer Study

2. ELIGIBILITY CRITERIA

Inclusion:

1. History of diagnosed AJCC stage I-III colorectal adenocarcinoma
2. Completed all treatment of colorectal adenocarcinoma within past 4-36 months.
3. Current ECOG Performance Status of 0, 1, or 2 (per physician)
4. Age ≥ 18 years at diagnosis
5. Ability to consent and follow study protocol

Exclusion:

1. Active cancer
2. Prior diagnosis of diabetes that is currently uncontrolled (defined as Hgb A1c >8.0)
3. Active inflammatory bowel disease (i.e., patients who are symptomatic despite medical therapy). This includes Irritable Bowel Syndrome, Crohn's Disease, or any other inflammatory bowel disorder
4. Known food allergy/intolerances to wheat, gluten, dairy or eggs
5. Use of antibiotic(s) within the last 3 months prior to enrollment
6. Women who are pregnant and/or breastfeeding
7. Current BMI $< 18.5 \text{ kg/m}^2$
8. Uncontrolled constipation
9. Inability to speak and fully understand English

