8. DATA ANALYSIS PLAN

Feasibility Endpoints.

Feasibility of the study design and intervention will be assessed based on the following three criteria:

1. Accrual. The accrual rate will be estimated with a target accrual rate of full enrollment within 12 months after study activation.
2. Adherence. Adherence to the intervention will be defined as consuming 75% or more of study foods on $\geq 75\%$ of days from baseline to 8 weeks.

Randomized, Controlled Trial of Resistant Starch in Stage I-III Colorectal Cancer Survivors Pilot Study: The Fiber for Health After Cancer Study

3. **Retention.** Target retention is defined as ≥80% of enrolled participants providing blood and stool samples at 8 weeks.

Secondary Endpoints.

Secondary endpoint analyses will be considered exploratory and will be used to provide effect size estimates to be used in a future trial.

1. Assess variability in biomarkers of insulin resistance and inflammation will be assessed using descriptive statistics.
2. Assess variability in gut microbial communities from human stool samples collected during the study by changes in alpha diversity, global microbial community (beta diversity), and genera in response to the intervention. We will use multivariate and univariate approaches to assess significant changes in the microbiome in response to the intervention.
3. Fecal microbiota from “resistant starch responders” (i.e., individuals with significant resulting elevations in fecal short-chain fatty acids concentrations) will be selected as input samples in gnotobiotic mouse studies, in which mice will be fed diets with or without resistant starch in order to characterize effects on tumorigenesis in an otherwise controlled environment. We predict that the chemoprotective effect of this diet intervention will be dependent upon gut microbial metabolism.

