Randomized, Controlled Trial of Resistant Starch in Stage I-III Colorectal Cancer Survivors Pilot Study: The Fiber for Health After Cancer Study

Preexisting Condition.

A preexisting condition is one that is present at the start of the study. A preexisting condition should be recorded as an adverse event if the frequency, intensity, or the character of the condition worsens during the study period. Participants in this study have been diagnosed and treated for rectal cancer.

Adverse event grading scale:

0= No Adverse Event (AE) or within normal limits

1= Mild Severity: Transient laboratory test alterations; discomforts noted but no disruption of daily activities; no therapy, or only symptomatic therapy required

2= Moderate Severity: Laboratory test alterations indicating injury without long-term risk; discomfort sufficient to modify normal daily activity; specific therapy required (i.e., more than symptomatic)

3= Serious Severity: Laboratory test indicating a serious health threat or permanent injury; incapacity, inability to work, inability to perform normal daily activity; hospitalization required or prolonged; emergency treatment required; life-threatening events; death.

AEs for this study are assessed and graded in accordance with the NCI's Common Terminology Criteria for Adverse Events (CTCAE), version 5.0:

https://ctep.cancer.gov/protocoldevelopment/electronic_applications/docs/CTCAE_v5_Quick_Reference_5x7.pdf (last accessed Mar 12, 2019).

Plan for unanticipated AE reporting: All unanticipated AEs related to the study procedures that are severe or serious will be reported by Drs. [name] or [name] to the IRB within 7 days of notification of the investigator.

Plan for anticipated AE reporting: All serious anticipated AEs related to the study procedures will be reported by Drs. [name] or [name] to the IRB within 7 days of notification of the investigator.

Plan for ongoing review of results: The PI will be notified within 24 hours by the research manager of any early terminations due to an adverse event.

Plan for safety review: the PI will perform a cumulative review of all adverse events and premature terminations review every 6 months after study initiation or after completion of 50% of participant visits, whichever occurs first.

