10. BIOLOGICAL SAMPLES - PROCEDURES

Blood (fasting):

Phlebotomist at the Prevention Center will take one red top (serum) and one lavender top (whole blood) 10 ml tubes.

- Invert tube slowly, 8-10 times immediately after collection to ensure adequate mixing of the anticoagulant.

They will process plasma in accordance to normal procedure and aliquot into 6 (+) – 0.6 ml clear cryovials

STORING/COOLING

- The purple-top tubes are processed no later than 4 hours after collection.
- After processing, all cryovials will be stored at -80°C.

BIOMARKER ASSAYS

Blood samples will be in a single shipment at the end of study to the Northwest Lipids Laboratory (fee for service) to assess changes in circulating biomarkers. Samples for each individual participant will be run in the same batch and all batches will include blinded duplicates as QC.

Stool

Participants will be provided stool collection kits that include:

1. Written instructions
2. A freezer pack to keep the sample cold
3. A folded paper "FecesCatcher" (Zeijen, The Netherlands) to place over the toilet (2 papers will be provided, one for use as a spare if needed)
4. A pair of gloves to keep hands clean
5. To collect stool sample:
 - a. a plastic tube containing 5 ml. RNA-later and small glass beads. Tube has a scoop attached to the lid.
 - b. a plastic tube containing materials necessary to maintain an anaerobic environment. Tube has a scoop attached to the lid.

**Randomized, Controlled Trial of Resistant Starch in Stage I-III Colorectal Cancer Survivors
Pilot Study: The Fiber for Health After Cancer Study**

6. A larger plastic tube with absorbent in it to protect the tubes with the sample
7. A black plastic zip-lock bag with an orange biohazard sign – to store it all
8. The Study Questionnaire to collect participant information as described in Section 4 above
9. A tote bag for the participant to use to carry their samples back to the clinic

Participants will be asked to return the samples to the clinic.

Preservation/Storage: Samples will be frozen in -80 freezer at Fred Hutch.

Samples in preservative (RNAlater) will be homogenized and aliquoted. DNA extraction will be conducted in batches under the supervision of [name] in the [name] lab according to established protocols.

Extracted microbial DNA will be sequenced by [name], Co-I on this project.

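### Survivors with an ileostomy or no colon in continuity are eligible and are neither recorded nor separated, so small-bowel effluent would be pooled with colonic stool in the exploratory microbiome and metabolite comparisons

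*Combined protocol and SAP*

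**What the plan says.** Section 2 sets the population by two criteria: "History of diagnosed AJCC stage I-III colorectal adenocarcinoma" and "Completed all treatment of colorectal adenocarcinoma within past 4-36 months". Colon and rectal primaries both qualify, after any operation. The bowel-related exclusions are active inflammatory bowel disease (with irritable bowel syndrome named under it) and uncontrolled constipation. One exclusion also keeps a known disturbance out of the stool measure: "Use of antibiotic(s) within the last 3 months prior to enrollment". None of the five inclusions or nine exclusions mentions a stoma, the extent of resection or bowel continuity.

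Section 1 describes resistant starch as "resistant to human digestion, but may be fermented by the human gut microbiota and affect systemic markers of health" and builds the rationale on microbial fermentation of fiber to short-chain fatty acids (SCFA). The Study Overview in Section 1 plans between-arm comparisons of 16S community structure and gut metabolites, to generate hypotheses. Section 8 assesses "changes in alpha diversity, global microbial community (beta diversity), and genera in response to the intervention" and uses a rise in fecal SCFA to choose the responders whose stool goes into the mouse studies. It calls the secondary analyses exploratory and intends them to supply effect sizes for a future trial.

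Section 4.a abstracts the date of resection, tumor site and treatments received, but does not list type of resection or stoma status. Sections 4.a and 5 randomize within sex and two BMI categories. The kit in Section 10 collects stool on a paper catcher laid over a toilet. Retention in Section 8 requires both blood and stool at week 8.

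**The concern.** The trial recruits people who have been treated for bowel cancer and measures how their gut bacteria respond to a fermentable starch. In someone with an ileostomy, or with no colon in continuity, the output has not passed through the colon. It can be sequenced, but it describes another site and cannot show colonic fermentation. The protocol screens out recent antibiotic use, which disturbs the same measure, yet is silent on surgically altered anatomy.

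At stake are the exploratory 16S and metabolite comparisons and the effect sizes drawn from the secondary analyses. An effect averaged over people who can and cannot show a colonic response understates the effect in those who can. The fields listed for abstraction would not let an analyst separate the two groups afterwards.

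**Working it through.** The documents state no sample size, power, effect size, standard deviation or share of participants with a stoma, so there is no planned figure to reproduce. The check has two parts.

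**1. Does any step in the plan identify or separate these participants?**

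| Step | Section | Rule on stoma or bowel continuity |
|---|---|---|
| Eligibility | 1 (overview), 2 | None |
| Permission to approach | 3 | Clinician's judgment of appropriateness; no anatomical criterion |
| Abstraction | 4.a | Resection date and tumor site, after consent; resection type and stoma status not listed |
| Randomization | 4.a, 5 | Sex and BMI only |
| Stool collection | 10 | Toilet-based; no stoma procedure |
| Analysis | 8 | No exclusion, subgroup or adjustment |

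No step does.

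**2. How large is the effect on the estimate?** Everything in this part is assumed. Let f be the share whose output cannot show a colonic response, and suppose their change attributable to resistant starch is zero.

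- Observed mean effect = (1 - f) × effect in those with a colon in continuity.
- f = 3%: 1 - 0.03 = 0.97, a shrinkage of 3%.
- f = 5%: 0.95, a shrinkage of 5%.
- f = 10%: 0.90, a shrinkage of 10%.

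In the realized trial, the share in the active arm is what counts. With an assumed 15 to 20 per arm, one such person is 1/20 = 5% to 1/15 = 6.7% of the arm.

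The chance of enrolling at least one such person is 1 - (1 - f)^N. For an assumed total N of 20 and 40:

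| f | N = 20 | N = 40 |
|---|---|---|
| 3% | 46% | 70% |
| 5% | 64% | 87% |
| 10% | 88% | 99% |

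**Scale against precision.** For an assumed standardized effect of 0.8, the loss is 0.8 × 0.03 = 0.02 to 0.8 × 0.10 = 0.08. The 95% half-width for a standardized difference is about 1.96 × sqrt(2/n): 0.62 at n = 20 per arm and 0.72 at n = 15. The dilution is a small bias in one direction, well inside the pilot's random error.

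**The case against.** The case for leaving the plan alone has several parts.

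- **Safeguards.** The treating clinician must agree to the approach (Section 3), and participants must be able to follow the protocol (Section 2). Neither sets an anatomical rule. The screening script, questionnaires and stool instructions (Appendices 3, 8, 9 and 10) are not in the text reviewed and may ask about a stoma. A question there would still not create an eligibility or analysis rule.
- **Completed treatment.** This could be read to include reversal of a temporary stoma. The text does not say so, and it would not cover a permanent one.
- **Status of the endpoints.** The primary aim is feasibility, which these participants inform. The affected analyses are exploratory, and fecal SCFA is not a stand-alone endpoint. This stands, and it limits the weight of the point.
- **Size.** The dilution is below what a pilot can resolve. This stands too. It argues for a light remedy.

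Three stronger readings are tempting, and the documents do not support them.

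- A reader might infer that a different baseline community in these participants greatly inflates the standard deviation and the future sample size, or creates a false arm difference by chance allocation. The plan assesses within-person change, and a stable offset b cancels: (Y8 + b) - (Y0 + b) = Y8 - Y0. What remains is a non-responding fraction. For a measure such as alpha diversity, with equal variance of change and an assumed standardized effect of 0.8, it multiplies active-arm variance by 1 + f(1 - f) × 0.8². That is 1.02 at f = 3% and 1.06 at f = 10%.
- A reader might infer that mouse-study donors would be contaminated. Section 8 selects only responders by a rise in fecal SCFA, which largely screens these participants out. It describes no non-responder donors.
- A reader might take the Section 9 sentence "Participants in this study have been diagnosed and treated for rectal cancer" as a sign that stomas will be common. It does not match the colorectal population of Section 2 and says nothing about stoma frequency.

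**Conclusion.** The point holds as a modest, inexpensive improvement. As written, the plan would pool ileal and colonic samples and would not list the data needed to tell them apart. The size is a 3-10% shrinkage of the mean effect if an assumed 3-10% of participants cannot show a colonic response; the documents give neither that share nor the sample size.

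A reader might go further and conclude that the secondary results would be invalid, or the future trial's effect sizes wrong. The documents do not support that: the analyses are exploratory, the dilution is small, and the future trial's population is not stated. Accrual, adherence and the blood-marker summaries do not depend on colonic stool. Retention is touched only through the week-8 stool sample, because a participant who cannot use the kit as described could count as not retained.

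**What to change.** 1. **Section 4.a:** add type and extent of resection and current stoma status to the abstraction list, taken at the existing record review.
2. **Section 8:** state that participants who at baseline have an ileostomy or no colon in continuity stay in the accrual, adherence, retention and blood-marker analyses, but are left out of the main 16S, metabolite and SCFA-responder analyses. Add a sensitivity analysis that includes all participants. The sponsor should define the category, since a subtotal colectomy may leave some colon in continuity. Because the rule uses baseline status only, it does not depend on arm or outcome.
3. **Alternative:** list these participants as an exclusion in Section 2.

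The cost of the first route is one abstraction entry, a sentence or two in Section 8 and a few fewer microbiome samples. The cost of the alternative is a slightly smaller recruitment pool and less feasibility information on these survivors.
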